1 STUDY SYNOPSIS

Complete Protocol Title	A multi-Centre, Prospective Study to Obtain Survival and Clinical Outcome Data on the Zimmer Hip Resurfacing System utilising the Metasul Monoblock Component (MMC) cup in a Hip Resurfacing Application with the Durom Hip Resurfacing Femoral Component
Protocol Number	09-H00
Short Protocol Title	MMC Resurfacing Study
Sponsor	Zimmer GmbH
Manufacturer	Zimmer GmbH
Study Device(s)	Zimmer Hip Resurfacing System (MMC Cup and Durom resurfacing femoral component)
Study Objectives/Endpoints	
The objective of this study is to obtain survival and outcome data on the Zimmer Hip Resurfacing System.
 
This will be assessed by analysis of standard scoring systems, radiographs and adverse event records. Data will be used to monitor pain, mobility and survivorship, and to confirm the safety and efficacy of the Zimmer Hip Resurfacing System.
 
Serum metal ion levels (cobalt and chromium) will also be collected pre-operatively and again at 6 months, 1 year, 2 years and 5 years.

Indications/Target Population	
The Zimmer Hip Resurfacing System is designed for the treatment of degenerative diseases or trauma of the hip. The system is intended to reduce pain and increase hip mobility
 
The Zimmer Hip Resurfacing System may be used for the following indications:
 
➤ Non inflammatory degenerative joint disease (NIDJD), e.g. avascular necrosis, primary osteoarthritis and post traumatic arthritis
 
➤ Inflammatory joint disease (IJD), e.g. rheumatoid arthritis

Inclusion/Exclusion Criteria	
Inclusion Criteria
 
After patient eligibility is established and the patient has signed the Ethics Committee approved Informed Consent, the patient must meet the following Inclusion/Exclusion criteria to participate in the clinical study.
 
1. Patient selection without bias to race or gender.

	
2. Patient is ≥ 18 and ≤ 65 years of age.3. Female patients only, if
a. Actively practicing a contraceptive method, orb. Surgically sterilized, orc. Post-menopausal4. Pre-operative Harris Hip Score ≤ 70.5. Primary surgical hip candidate, suffering from hip pain and/or disability due to degenerative joint disease (inflammatory or non-inflammatory), based on physical examination and history, which may include the following diagnosis:
a. Non-inflammatory degenerative joint disease (NIDJD), e.g. avascular necrosis or osteoarthritisb. Inflammatory joint disease (IJD), e.g., rheumatoid arthritis6. Patient is willing and able to cooperate in prescribed post-operative therapy.7. Patient is willing and able to complete scheduled follow-up evaluations as described in the Informed Consent.8. Patient has participated in the Informed Consent process and has signed an Ethics Committee approved Informed Consent.
--	---

Exclusion Criteria

	
1. Patient has an acute, chronic, local or systemic infection.2. Patient is skeletally immature.3. Patient is known to be pregnant.4. Patient has a severe muscular, neural or vascular disease that endangers the involved extremity.5. Patient has an insufficient acetabular or femoral bone stock in which good anchorage of the implants are unlikely or impossible, including, but not limited to:
a. patient with severe osteopenia,b. patients with a family history of severe osteoporosis or osteopenia,c. patients with osteonecrosis or avascular necrosis (AVN) with $>50\%$ involvement of
--	---

	
the femoral head (regardless of FICAT grade), or
 
d. patients with local bone tumors and/or cysts of the femoral head > 1 cm
 
6. Patient has a total or partial absence of the muscular or ligamentous apparatus.
 
7. Patient has known moderate to severe renal insufficiency.
 
8. Patient has a known clinical condition which may interfere with the patient's outcome, including but not limited to:
 
a. immuno-compromised conditions (AIDS),b. organ transplant,c. high doses of corticosteroids etc 
9. Patient is severely overweight (BMI > 40)
 
10. Patient is scheduled for simultaneous bilateral total hip replacement.
 
11. OPERATIVE (IPSILATERAL) HIP: Patient has a total prosthetic hip replacement device, surface arthroplasty, endoprosthesis or femoral and/or acetabular osteosynthesis.
 
12. CONTRALATERAL HIP: Patient has had a hip replacement, surface arthroplasty or endoprosthesis, within the past 12 months, unless previously enrolled in this clinical study.
 
13. Patient is:
 
a. a prisoner,b. mentally incompetent,c. a known alcohol or drug abuser,d. anticipated to be non-compliant 
14. Patient has participated in a study of any other investigational device (drug, device or biologic) within the past 12 months. Exception: previous enrollment in the Zimmer Hip Resurfacing clinical study.
 
15. Patient has a known allergy to one of the constituents of the implant, e.g. cobalt, chromium, nickel, etc.

Study Design	A multi-centre, prospective, non-randomised post-market study. To reduce bias a consecutive case series will be

	recruited. Patients will receive the Zimmer Hip Resurfacing System.
Clinical Phase	Post-market
Sample Size	A total of 100 patients will be enrolled into the study
Length of Study	11 years, 10 year follow-up with 1 year to recruit. Follow-up visits at 6 months, 1, 2, 3, 5, 7 and 10 years post-operatively.
Materials and Methods	Case report forms will be completed either in-office, hospital or by phone or mail at Pre-op, Surgery, 6 months, 1-year, 2-year, 3-year 5-year, 7-year, and 10-year intervals.
Data Collection	Paper
Statistical Reporting	Data collected will be summarised and reported to each participating Investigator. Statistical analysis is conducted by Zimmer or its designee.
Scores/Performance Assessments	Safety will be assessed by appropriate recording and reporting of adverse events throughout the study. All system components are CE marked and commercially available.
Standards	
The PMCF is compliant with the below:
 
• ISO 14155: 2020 - Clinical investigation of medical devices for human subjects - Good clinical practice.• The Declaration of Helsinki (DoH) - Ethical principles for medical research involving human subjects. 
(*) The study protocol was drafted according to another version of the ISO 14155. Adverse Event definitions and reporting are according to ISO 14155:2020.

Study Funding	Funding for this clinical study is made available by Zimmer Biomet to support clinical data collection, IRB/EC review fees and other expenses associated with the conduct and execution of this study protocol as outlined in the fully executed Clinical Trial Agreement.

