2 STATISTICAL ANALYSIS PLAN

2.1 Sample Size

The primary endpoint for this study (in the following 'experimental group') is implant survival at 10 years which is assessed by revision of the Metasul Monoblock Component Cup. A success rate for the experimental group will be calculated using the Kaplan-Meier Survival Estimation. A success rate of the experimental group of 92.5% at 10 years is assumed, equivalent to the survival rate of the historical group. The historical value is based on figures on ten-year survival data from the Australian Orthopaedic Association National Joint Replacement Registry[10]. Accordingly, a sample size of 80 achieves a 95% confidence interval of 86.7% to 98.3%. A sample size of 100 allows for a yearly attrition rate of 2% over the estimated 10-years period. This sample size estimation was calculated with PASS 11, NCSS, LLC. Kaysville, Utah

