2.2 Statistical Analysis

Data collected in the study will be summarised descriptively. Descriptive summaries will be the basis of study reports to participants, as well as to generate an overall summary of the clinical performance of the Zimmer Hip Resurfacing System and may be used for reports and to support presentations and publications as needed.

Summaries will routinely describe categorical data as counts and percentages, and ninety-five percent confidence limits will be generally used to assess differences over time. Routine summaries describing continuous data will be in the form of means, medians, standard deviations, minima, and maxima, and ninety-five percent confidence intervals will be used to understand those time differences.

Routine summaries of implant survival, return to function, etc. (e.g., time to event) will be described via the Kaplan-Meier method and these will be accompanied with the corresponding crude rates (expressed as percentages). Routine summaries of complication data will be in the form of frequencies and percentages. Summaries may be further generated for strata within the study population, (e.g., males and females, at different cut-points in the body mass index continuum, etc.).

Patient confidentiality will be protected at all times, and patient identifiers will not be included in study summaries.

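### Does a plan that speaks of confirming safety and efficacy need a success criterion against the historical 92.5%?

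*Combined protocol and SAP*

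**What the plan says.** The Study Objectives/Endpoints entry of the synopsis (section 1) opens with: "The objective of this study is to obtain survival and outcome data on the Zimmer Hip Resurfacing System". A later sentence on how the data will be used adds monitoring of pain, mobility and survivorship, and then the phrase "to confirm the safety and efficacy of the Zimmer Hip Resurfacing System".

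In section 2.1 the primary endpoint "is implant survival at 10 years which is assessed by revision of the Metasul Monoblock Component Cup". The planning value is given as: "A success rate of the experimental group of 92.5% at 10 years is assumed, equivalent to the survival rate of the historical group". The number of patients is justified by precision: "a sample size of 80 achieves a 95% confidence interval of 86.7% to 98.3" (per cent). Enrolment is then raised for dropout: "A sample size of 100 allows for a yearly attrition rate of 2% over the estimated 10-years period". The estimator is also named: "A success rate for the experimental group will be calculated using the Kaplan-Meier Survival Estimation".

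Section 2.2 begins: "Data collected in the study will be summarised descriptively". It applies 95% limits to changes over time and Kaplan-Meier to implant survival. Neither section states a hypothesis, margin, performance goal, minimum lower limit or power, and neither promises a formal comparison with 92.5%.

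**The concern.** Confirming something normally requires a result, fixed in advance, that would count as failure. Here the cohort is called experimental, a historical group is named beside it, and the two are assumed equal. A reader then expects a comparison and finds none. Two informal readings could fill the space:

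- **The interval covers 92.5%.** This treats absence of a detected difference as agreement. With about 80 patients a clearly worse device could pass.
- **The lower limit exceeds 92.5%.** A device exactly as good as the registry figure would almost never pass.

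At stake would be a post-market report that claims agreement with the registry for an implant whose failure rate is well above the assumed 7.5%.

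**Working it through.** **Inputs.** From section 2.1: survival p = 0.925, n = 80 evaluable, 100 enrolled, attrition 2% a year for 10 years, two-sided 95% confidence. The method for the Kaplan-Meier interval is not stated.

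**Step 1: reproduce the plan's figure.** The simple normal (Wald) interval is p ± 1.96 × √(p(1 − p)/n).

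- √(0.925 × 0.075 / 80) = 0.02945, and 1.96 × 0.02945 = 0.0577.
- 92.5% ± 5.8 points gives 86.7% to 98.3%, as printed.
- Attrition: 80 / (1 − 0.20) = 100, or 80 / 0.98^10 = 97.9 if compounded. Both agree with 100 enrolled.

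The sizing is therefore a precision calculation and is internally correct.

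**Step 2: test the imputed rule that the interval should cover 92.5%.** The half-width must be recomputed at each observed value. At 68/80, √(0.85 × 0.15 / 80) = 0.0399, and 1.96 × 0.0399 = 0.078, so Wald gives 77.2% to 92.8%. Upper 95% limits with n = 80:

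| Observed | Wald | Exact (Clopper-Pearson) | Wilson |
|---|---|---|---|
| 68/80 = 85.0% | 92.8% | 92.0% | 91.2% |
| 69/80 = 86.3% | 93.8% | 92.9% | 92.2% |
| 70/80 = 87.5% | 94.8% | 93.8% | 93.1% |

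At 85% the result depends on the method: Wald reaches 92.5% by 0.3 points, and exact and Wilson do not. Kaplan-Meier also credits partial follow-up of all 100 patients. Assuming constant hazard and 2% yearly loss, the Greenwood variance at 85% corresponds to about 90 patients. The plain interval is then 77.6% to 92.4%, which just misses 92.5%. The log-log upper limit is 90.9% and the log upper limit 92.7%. At 87.5% all three n = 80 methods in the table include 92.5%.

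**Step 3: how often each informal reading would be met (binomial, n = 80).**

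| True survival | Wald upper limit ≥ 92.5% | Exact | Wilson |
|---|---|---|---|
| 87.5% | 80% | 70% | 58% |
| 85.0% | 58% | 45% | 33% |

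For the opposite reading, the exact lower limit exceeds 92.5% only at 79 or 80 of 80 unrevised. If true survival is 92.5%, that happens in 1.5% of trials.

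**Step 4: set these against what the plan undertakes.** Neither reading is written in section 2.1 or 2.2. In section 2.1 the 92.5% is the value at which the interval width was calculated. The synopsis links its use-of-data sentence to scores, radiographs and adverse event records, not to a survival threshold. What the plan commits to is an estimate of 10-year survival with its uncertainty, and steps 1 to 3 leave that untouched.

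**The case for a change.** The strongest case for a change runs as follows. The synopsis commits the data to confirmation, section 2.1 invites comparison by naming a historical group, and section 2.2 lets the summaries support publications. A single-arm post-market design does not by itself supply a criterion. One sentence would close the gap at no cost in patients or data: either claim only estimation, or fix a floor for the lower limit before the 10-year result is known.

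Much of this stands. No criterion exists, and step 3 shows that covering 92.5% would be weak evidence of agreement. Anyone who reports it as confirmation would be overreaching.

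What does not stand is that the plan needs repair. Moving the wording to estimation brings a secondary sentence into line with the objective already stated and changes no output. Adding a floor would turn a descriptive series into a hypothesis test. The documents offer no basis for choosing that floor, and the sample was not sized for one. As an illustration with an assumed margin, ruling out 85% (7.5 points below 92.5%) at one-sided 0.025 has about 44% to 46% power with 80 patients when true survival is 92.5%; 80% power would need about 151 evaluable. Whether to take that on is a design choice for the sponsor.

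**Conclusion.** No change is needed. The plan uses one word that is stronger than its design, but the stated objective, the precision-based sample size and the descriptive Kaplan-Meier analysis agree with one another. Followed as written, they give a sound estimate of 10-year survival, with a half-width of about 5.8 points if survival is near 92.5% and 80 patients are evaluable.

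The possible misreading is real but lies outside the plan. If coverage of 92.5% were taken as confirmation, an observed 87.5% (12.5% failures against the assumed 7.5%) would pass under the Wald, exact and Wilson intervals at n = 80. Observed survival of 85%, twice the assumed failure rate, would pass by Wald but not by exact or Wilson limits. These figures assume binomial data on 80 patients; with censoring they shift according to the Kaplan-Meier interval chosen. An analyst who reports the estimate and its interval, and does not present overlap with the registry value as equivalence, has done what the plan asks.

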2 STATISTICAL ANALYSIS PLAN

2.1 Sample Size

The primary endpoint for this study (in the following 'experimental group') is implant survival at 10 years which is assessed by revision of the Metasul Monoblock Component Cup. A success rate for the experimental group will be calculated using the Kaplan-Meier Survival Estimation. A success rate of the experimental group of 92.5% at 10 years is assumed, equivalent to the survival rate of the historical group. The historical value is based on figures on ten-year survival data from the Australian Orthopaedic Association National Joint Replacement Registry[10]. Accordingly, a sample size of 80 achieves a 95% confidence interval of 86.7% to 98.3%. A sample size of 100 allows for a yearly attrition rate of 2% over the estimated 10-years period. This sample size estimation was calculated with PASS 11, NCSS, LLC. Kaysville, Utah

2.2 Statistical Analysis

Data collected in the study will be summarised descriptively. Descriptive summaries will be the basis of study reports to participants, as well as to generate an overall summary of the clinical performance of the Zimmer Hip Resurfacing System and may be used for reports and to support presentations and publications as needed.

Summaries will routinely describe categorical data as counts and percentages, and ninety-five percent confidence limits will be generally used to assess differences over time. Routine summaries describing continuous data will be in the form of means, medians, standard deviations, minima, and maxima, and ninety-five percent confidence intervals will be used to understand those time differences.

Routine summaries of implant survival, return to function, etc. (e.g., time to event) will be described via the Kaplan-Meier method and these will be accompanied with the corresponding crude rates (expressed as percentages). Routine summaries of complication data will be in the form of frequencies and percentages. Summaries may be further generated for strata within the study population, (e.g., males and females, at different cut-points in the body mass index continuum, etc.).

Patient confidentiality will be protected at all times, and patient identifiers will not be included in study summaries.

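### Does SAP section 2.2 need to say that its 95% intervals for time differences are for within-patient change?

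*Combined protocol and SAP*

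**What the plan says.** Section 2.2 of the SAP sets out descriptive summaries. For categorical outcomes it first fixes the form of the table: "Summaries will routinely describe categorical data as counts and percentages". The same sentence then gives the interval its purpose: "ninety-five percent confidence limits will be generally used to assess differences over time". For continuous outcomes the form is: "Routine summaries describing continuous data will be in the form of means, medians, standard deviations, minima, and maxima". The purpose of the interval there is worded much as before: "ninety-five percent confidence intervals will be used to understand those time differences". Neither sentence names a reference visit, a change score, a paired method or a repeated-measures model, and nothing elsewhere in the document does.

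The synopsis (section 1) describes one non-randomised cohort seen repeatedly: "Follow-up visits at 6 months, 1, 2, 3, 5, 7 and 10 years post-operatively", in addition to the pre-operative assessment. On use of the data it says: "Data will be used to monitor pain, mobility and survivorship". The schedule for the two serum metal ions is that they "will also be collected pre-operatively and again at 6 months, 1 year, 2 years and 5 years". Section 2.1 plans for losses: "A sample size of 100 allows for a yearly attrition rate of 2% over the estimated 10-years period".

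**The concern.** The listed summaries can all be computed one visit at a time. A reader could therefore expect a table with a mean or percentage and its 95% limits at each visit, with change judged by comparing rows. That would fall short in two ways.

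- Limits on two separate estimates are not limits on their difference. They ignore that the same patients are measured at both times, and a reader who looks for overlap between them applies a much stricter standard than 5%.
- Later rows contain fewer patients than the pre-operative row, so a difference between rows can mix real change with a change in who is measured.

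With no control group, change from the pre-operative state is the main internal comparison for pain, mobility and metal ions. A blurred interval could hide a modest late decline in a score or a modest rise in ions.

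**Working it through.** **Inputs.** From section 2.1: 100 enrolled, 80 evaluable at 10 years, 2% attrition a year, assumed 10-year survival 92.5%. The documents give no SD and no between-visit correlation *r*. Results below are therefore in SD units, with equal SDs at both visits and *r* assumed over a range.

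**The plan's own figures.** The only interval stated is for the primary endpoint: 0.925 ± 1.96 × √(0.925 × 0.075 / 80) = 0.925 ± 0.058, or 86.7% to 98.3%. This agrees with section 2.1. Attrition agrees too: 100 − 10 × 2 = 80 (compounded, 100 × 0.98^10 = 81.7). Neither figure involves the time-difference intervals.

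**What per-visit limits would give, n = 80.**

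- One visit's mean: 1.96 / √80 = 0.219 SD, whatever *r* is.
- Within-patient change: 1.96 × √(2(1 − *r*) / 80).

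| Assumed *r* | Half-width, one visit | Half-width, change |
|---|---|---|
| 0 | 0.219 | 0.310 |
| 0.3 | 0.219 | 0.259 |
| 0.5 | 0.219 | 0.219 |
| 0.7 | 0.219 | 0.170 |

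The widths agree only at *r* = 0.5, and even there the per-visit interval is centred on a visit mean, not on the change.

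**Judging by overlap.** Two per-visit intervals separate only when the means differ by 2 × 0.219 = 0.438 SD. The two-sided error rate of that rule is 2 × [1 − Φ(2 × 1.96 / √(2(1 − *r*)))], which is 0.0056 at *r* = 0 and 0.00009 at *r* = 0.5. A change that the paired interval would detect with 80% power is detected with 51% power at *r* = 0 and 13% at *r* = 0.5.

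**Treating the visits as independent.** An interval for the difference that ignores pairing is a separate possibility. With 100 pre-operative and 80 ten-year values its half-width is 1.96 × √(1/100 + 1/80) = 0.294 SD. At *r* = 0 this is slightly narrower than the paired 0.310. At *r* = 0.7 it is wider than the paired 0.170.

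**Who is measured.** If patients lost by a visit differ from those retained by *d* SD in pre-operative mean, comparing all pre-operative values with the retained patients' later values moves the difference by (fraction lost) × *d*. For assumed *d* = 0.2, 0.5 or 0.8:

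- at 5 years, 10% lost: 0.02, 0.05 or 0.08 SD;
- at 10 years, 20% lost: 0.04, 0.10 or 0.16 SD.

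The direction is unknown. The last planned ion sample is at 5 years, where the shift is at its smaller values.

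**Set against the text.** Both sentences in section 2.2 give the interval a purpose, and in both that purpose is the difference between times. Neither says that limits go on each visit's estimate. Means and SDs can summarise change scores as well as visit values. An analyst who reports the paired change with its own 95% interval, or a paired difference in proportions, contradicts nothing in the plan.

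**The case for a change.** The strongest case for amending runs as follows. Section 2.2 is the whole analysis text. It goes beyond pure description by using intervals to assess differences, and its output may feed publications and the synopsis's stated aim of confirming safety and efficacy. Naming the quantity in advance would stop anyone choosing between readings after seeing the results. It would cost a few words and no new data. Overlap reading is badly conservative even at zero correlation, and for metal ions a missed rise would matter.

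Much of this stands. The quantity is not named, per-visit limits would be the wrong tool for change, and the overlap figures are correct. What does not follow is that the plan calls for that tool. All of the loss lies in readings that the text does not require and that fit its stated purpose less well. No target change, margin or decision rule is set for scores or ions, so no planned conclusion can be shown to turn on the choice.

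The gain from pairing also depends on correlations that the documents do not give. It is nil or slightly negative at *r* = 0, and the entry limit on the pre-operative Harris Hip Score may keep the pre/post correlation low. Nor does a simple paired difference settle the attrition point: it estimates change among patients still followed, not among all who were enrolled.

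**Conclusion.** The concern correctly identifies an unstated detail, but not an error. Section 2.2 leaves open which quantity carries the 95% interval, and the reading that best fits its words, an interval for the difference, is the sound one. Under the per-visit reading the mismatch would be real: 0.219 SD against 0.170 to 0.310 SD at 10 years for *r* between 0.7 and 0, assuming 80 patients and equal SDs. Patient loss could add up to 0.16 SD if lost and retained patients differed by as much as 0.8 SD before surgery.

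These amounts concern descriptive secondary summaries only. The 10-year Kaplan-Meier survival estimate, its planned precision and the sample of 100 are unaffected. The data for a within-patient analysis are already scheduled, and the choice can be made properly at reporting without departing from the plan. No change is needed.

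### Complications are summarised only as percentages with no stated denominator and no allowance for incomplete follow-up over 10 years

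*Combined protocol and SAP*

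**What the plan says.** Section 2.2 gives two kinds of outcome different treatment.

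- **Time-to-event outcomes:** "Routine summaries of implant survival, return to function, etc. (e.g., time to event) will be described via the Kaplan-Meier method", and these are to be "accompanied with the corresponding crude rates (expressed as percentages").
- **Complications:** "Routine summaries of complication data will be in the form of frequencies and percentages". Nothing is said about who is in the denominator, how patients lost to follow-up are counted, or whether time since surgery enters the summary.

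Section 2.1 defines the primary endpoint as "implant survival at 10 years which is assessed by revision of the Metasul Monoblock Component Cup" and names its estimator: "A success rate for the experimental group will be calculated using the Kaplan-Meier Survival Estimation". The same section allows for a "yearly attrition rate of 2% over the estimated 10-years period", which is how 100 enrolled patients are meant to leave 80.

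The synopsis lists confirmation of safety among the purposes of the data (Study Objectives/Endpoints), with adverse events recorded throughout the study (Scores/Performance Assessments). Section 2.2 makes the descriptive summaries the basis of study reports and possible publications.

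**The concern.** With 10 years of follow-up and expected losses, some patients will leave before a complication that they would have had. A percentage cannot handle them properly. If they stay in the denominator, they count as complication-free to 10 years. If they are dropped while patients with events are kept, the event-free group is depleted and the percentage rises.

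Kaplan-Meier deals with this for implant survival by censoring, but the plan names no counterpart for complications. Apart from implant survival, the complication percentage is the only safety summary that the plan specifies. Because its denominator is open, the same data could yield noticeably different figures, and the choice could be made after the data are seen.

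**Working it through.** **1. The plan's own figures (Section 2.1).** With 92.5% survival and 80 patients, the Wald interval is 0.925 ± 1.96 × √(0.925 × 0.075 / 80) = 0.925 ± 0.058, or 86.7% to 98.3%, as stated. Ten years at 2% is 20%, and 80 / (1 − 0.20) = 100, also as stated. The plan's attrition assumption is therefore clear and can be used below.

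**2. Inputs.**
- From the documents: 10 years of follow-up, 2% yearly loss, 100 enrolled, 7.5% revised by 10 years (100% − 92.5%).
- Assumed: a true 10-year complication risk of 20%, a constant hazard, loss independent of complications, and a second loss rate of 5% a year.

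**3. Formulas.** For true 10-year risk q and yearly loss a, let λ = −ln(1 − q)/10 and μ = −ln(1 − a).
- Observed events as a share of all enrolled: C = λ/(λ + μ) × [1 − exp(−10(λ + μ))].
- Followed event-free to 10 years, as a share of all enrolled: E = (1 − q)(1 − a)^10.
- Percentage over patients with the event or followed event-free to 10 years: C/(C + E).

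**4. Complication with a true risk of 20%, 2% yearly loss.** λ = 0.02231 and μ = 0.02020.
- E = 0.80 × 0.98^10 = 0.6537.
- C = 0.02231/0.04252 × (1 − 0.6537) = 0.182.
- C/(C + E) = 0.182/0.835 = 0.218.

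Of 100 patients, about 18.2 have an observed event, 65.4 are followed event-free and 16.5 are lost first (rounded).

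**5. The same at 5% yearly loss (assumed).** μ = 0.05129.
- E = 0.80 × 0.95^10 = 0.479.
- C = 0.02231/0.07361 × (1 − 0.479) = 0.158.
- C/(C + E) = 0.158/0.637 = 0.248.

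| Yearly loss | True risk | Over all enrolled | Over event or event-free to 10 years |
|---|---|---|---|
| 2% (plan) | 20% (assumed) | 18.2% | 21.8% |
| 5% (assumed) | 20% (assumed) | 15.8% | 24.8% |

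Neither denominator recovers 20%, and the two err in opposite directions.

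**6. Revision, under the plan's assumptions.** With q = 7.5% and a = 2%, C = 6.8%, and the second denominator gives 8.3%. In 5,000 simulated trials of 100 patients, the mean Kaplan-Meier estimate was 7.5% (standard deviation 2.8 points) and the mean crude percentage over all enrolled was 6.8%. The planned primary estimator is therefore unaffected; only the crude companion figure reads low.

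**7. Timing of events.** Replacing the constant hazard in step 6 by Weibull shapes from 0.5 (early events) to 3 (late events) gives crude percentages from 7.0% to 6.5%, or 6% to 14% too low in relative terms. Early events are affected less.

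**The case against.** Four arguments can be made for the plan.

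- **The denominator is not stated, so no particular bias is established.** This is right as to direction. Section 2.2 also says that confidence limits will be used to look at changes over time in categorical data, which is compatible with denominators set at each visit. But step 5 of the working shows that the choice matters, so leaving it open is itself the gap.
- **The Kaplan-Meier sentence is open-ended and does not exclude complications.** True, but it does not commit the plan to them either, and the next sentence gives complications a method of their own.
- **The effect is small.** At the planned attrition the gap over all enrolled is 20 − 18.2 = 1.8 points. The binomial standard error at 100 patients is √(0.20 × 0.80 / 100) = 4.0 points. This stands, and it keeps the severity low.
- **The study is single-arm and descriptive, with no planned comparison of complications.** This also stands.

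A reader might infer three stronger things that the documents do not support.

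- **That revision risk is understated too.** It is not: Kaplan-Meier is the primary estimator, and the crude rate only accompanies it.
- **That the bias always favours the device.** This would need an all-enrolled denominator, which the plan does not specify.
- **That interim reports are especially misleading.** Reports to investigators and participants are mentioned without timing, and a count of complications to date is not a 10-year risk unless it is presented as one.

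**Conclusion.** The point holds for complications, as a minor one. Section 2.2 specifies a summary that does not allow for the attrition that Section 2.1 expects, and it leaves the denominator undefined. At 2% yearly loss, an assumed 20% risk is misstated by about 9% in relative terms, downwards or upwards according to the denominator (18.2% or 21.8%). At an assumed 5% loss it is about 21% too low or 24% too high (15.8% or 24.8%).

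These sizes rest on a constant hazard, loss independent of complications and the assumed 20% risk. If loss were related to complications, they would not apply as they stand. For revision, what remains is a matter of labelling: about 6.8% printed beside 7.5%, under the plan's assumptions and an all-enrolled denominator.

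**What to change.** In Section 2.2:

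- Keep the complication counts, and state the denominator of every percentage.
- For each main complication, add the cumulative incidence of first event at the scheduled visits (6 months, 1, 2, 3, 5, 7 and 10 years), with numbers at risk and 95% confidence intervals. Events per 100 patient-years with a 95% confidence interval is an acceptable alternative.
- Do not present a percentage of patients followed to a visit as a cumulative risk, because that denominator can overstate it.
- For revision, leave the Kaplan-Meier analysis as it is. State the denominator of the crude percentage and label it as unadjusted for follow-up.

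The cost is a few sentences of SAP text and a little programming; no extra patients or visits are needed. It does require complication onset dates and last-contact dates. The text available does not show a field for complication onset, so this should be confirmed; Kaplan-Meier for revision already needs dates of that kind. The reported complication figures may turn out slightly less favourable than an all-enrolled percentage would be.
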